2. BACKGROUND AND RATIONALE

2.1 Background

Endoscopic ultrasound (EUS) guided fine needle aspiration (EUS-FNA) is the primary technique for tissue acquisition for pancreatic lesions. Despite widespread adoption of the techniques, the diagnostic yield of EUS-FNA for pancreatic lesion is highly variable, with sensitivities ranging from 64-95%, specificities ranging from 75-100% and overall diagnostic accuracy ranging from 78-95%.

Despite its mainstay as the primary technique for tissue acquisition, EUS-FNA has several limitations. The standard EUS-FNA does not routinely provide core biopsy specimen with preserved tissue architecture, which is required for immunohistochemical staining and for definitive diagnosis of conditions, such as lymphoma, gastrointestinal stromal tumors, IgG-4-associated lymphoplasmacytic sclerosing pancreatitis. Furthermore, the diagnostic yield of EUS-FNA is highly dependent on the availability of bedside cytotechnologist or cytopathologist for rapid onsite evaluation (ROSE), which increases the overall cost required to perform EUS-FNA.

Recently, multiple dedicated EUS fine needle biopsy (FNB) needles have been developed to obtain core specimens. Early small studies have shown promising results with these EUS-FNB needles (1-6).

The objective of this single center paired cohort study is to evaluate the diagnostic accuracy of EUS-FNA with ROSE compared to EUS-FNA with ROSE. If EUS-FNB

without ROSE is shown to be non-inferior to the current standard of care of EUS-FNA with ROSE in pancreatic lesions, this study has the potential to make EUS-guided tissue acquisition more economical (with elimination for the need for cytopathology staff onsite) as well as provide core histological specimen without sacrificing the overall diagnostic yield.

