7. PROCEDURE PLAN

All EUS/FNB and EUS/FNA will be performed using a linear array echoendoscope by one of seven experienced EUS physicians at JHH. All patients will undergo both EUS/FNB and EUS/FNA. Patients will be randomized to either FNB or FNA first by

means of computer-generated numbers. The endoscopist will not be blinded to the randomization; however, the study pathologist will be blinded to randomization.

EUS/FNB will be performed using similar techniques for tissue acquisition as FNA using 22-g FNB needle (Medtronic SharkCore or Boston Scientific Acquire). Lesions will be identified using EUS and punctured with the 22-g FNB needle (10-15 back and forth movements per needle pass, fanning as appropriate). After the lesion is punctured, the stylet will be removed and 10cc suction will be applied. FNB samples will be placed directly into formalin containers and sent to be processed by surgical pathology.

EUS/FNA with ROSE will be performed using standard techniques via 22-g FNA needle (Cook Medical EchoTip Ultra or Boston Scientific Expect or Medtronic Beacon). Lesions will be identified using EUS and punctured with the FNA needle (10-15 back and forth movements per needle pass, fanning as appropriate). After the lesion is punctured, the stylet will be removed and 10cc suction will be applied. FNA specimens will be processed for ROSE using standard techniques with bedside smear slide evaluation and liquid-based cytology and cell-block preparation.

The first randomization assigned EUS sampling technique will be used until adequate specimen is achieved (up to 3 passes total). After 3 passes, the patient will undergo the other EUS sampling technique until adequate specimen is achieved (up to 3 passes total). If inadequate biopsies are obtained after a total of 6 passes (3 with initial tissue acquisition techniques, 3 with the other technique), the endosonographer will be permitted to utilize any EUS sampling technique preferred to obtain a diagnosis during the same procedure or at a later date.

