12. STATISTICAL CONSIDERATIONS

Overview: This study is designed as a non-inferiority trial.

Considering a success rate of 85% in the FNA with ROSE group, based published studies, we selected a non-inferiority margin (∂) of 10%, in accordance with the USFDA recommendations (8). Based on the following formula (9):

n = f(α, β) × [πs × (100 – πs) + πe × (100 – πe)] / (πs – πe – d)2

where πs and πe are the true percent 'success' in the standard and experimental treatment group respectively, and

 $f(\alpha, \beta) = [\Phi - 1(\alpha) + \Phi - 1(\beta)]2$

 Φ -1 is the cumulative distribution function of a standardized normal deviate

We calculated that our trial will require enrolling 120 patients for power of 80% and two sided α of 0.05.

Taking into consideration a 10% dropout rate, the total patients to be enrolled=132

Baseline demographics, pre-, intra- and post-intervention data will be prospectively collected on data collection forms which will be maintained in an electronic database system. Results will be reported as mean ± standard deviation (SD) for quantitative variables and percentages for categorical variables. The groups will be compared using the Student's t- test or Wilcoxon rank sum test for continuous variables and the chi-square test (or Fisher's exact test if required) for categorical variables. To compare

diagnostic accuracy between two EUS sampling techniques, we will use McNemar's test. Statistical significance will be based on two-sided design-based tests evaluated at α = 0.05. All statistical analyses will be performed using STATA.

a. Endpoints:

Primary:

Diagnostic accuracy will be defined as (true positive + true negative)/all samples. The final diagnosis will be based on one of the following criteria: (i) surgical pathology specimen from patients who underwent surgical resection; (ii) cytological or histopathological diagnosis of malignancy in patients with unresectable disease with appropriate imaging and clinical course of disease; (iii) cytological and histopathological diagnosis of benign disease with an appropriate clinical course of disease for minimum of 6 months.

Secondary:

1. Specimen adequacy

This will be defined as the proportion of samples in which a final histopathological diagnosis could be made.

2. Percentage of histology cores obtained

This will be defined as the proportion of samples in which a visible histology core biopsy was obtained

- 3. Number of passes Number of passes required for diagnosis

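### When FNA and FNB disagree in a patient with unresectable disease, the final diagnosis can rest on the malignant study reading itself, and no criterion allows a benign final diagnosis

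*Combined protocol and SAP*

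**What the plan says.** Section 12, under the primary endpoint, states: "Diagnostic accuracy will be defined as (true positive + true negative)/all samples". True and false are judged against a final diagnosis that can be reached by three routes:

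- Route (i): "surgical pathology specimen from patients who underwent surgical resection".
- Route (ii): "ii) cytological or histopathological diagnosis of malignancy in patients with unresectable disease with appropriate imaging and clinical course of disease".
- Route (iii): "cytological and histopathological diagnosis of benign disease with an appropriate clinical course of disease for minimum of 6 months".

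Section 7 makes the design paired: "All patients will undergo both EUS/FNB and EUS/FNA". FNA material goes to smears, liquid-based cytology and cell block; FNB material goes to surgical pathology. The analysis in section 12 is also paired: to compare "diagnostic accuracy between two EUS sampling techniques, we will use McNemar's test".

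On blinding, section 7 says that "the study pathologist will be blinded to randomization". It does not say whether a reader of one sample is blind to the result of the other, and no blinded or independent adjudication of the final diagnosis is described. Section 8 lists no follow-up visits and leaves longer follow-up to clinical need.

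**The concern.** Route (ii) accepts either type of tissue diagnosis and does not say that it must come from tissue other than the two samples under comparison. Every patient has both samples, so they are its natural source. Route (iii) needs both types to be benign and adds 6 months of observation. Route (ii) names no period and does not define what imaging or course would count as fitting.

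A paired accuracy comparison is driven by the patients in whom one technique is right and the other wrong. If a discordant pair is settled by one of the two readings, a false positive can become the reference against which the correct reading is marked wrong. The technique with more false positives then gains and the other loses. The trial asks whether FNB without ROSE is non-inferior to FNA with ROSE, so such a shift could favour or penalise FNB, depending on which technique has the lower specificity.

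**Working it through.** **Step 1. Where each discordant patient ends up.** Take one malignant and one benign reading and apply the three routes literally.

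| Patient | Route that applies | Scoring |
|---|---|---|
| Resected | (i), independent tissue | Correct |
| Unresectable, truly malignant, imaging and course fit | (ii) | Correct: the benign reading is a missed cancer |
| Unresectable, truly benign, check does not refute malignancy | (ii) | Wrong: false positive scored true positive, correct benign reading scored false negative |
| Unresectable, truly benign, check refutes malignancy | (ii) fails; (iii) fails because one reading is malignant | Unclassified |
| Resectable but not resected | (ii) does not cover it; (iii) fails | Unclassified |

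Without resection, no row scores a malignant reading as a false positive.

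**Step 2. Effect of one pair.** The documents give no figure for this bias. I use the stated 120 patients before dropout as the denominator (120 × 1.1 = 132, the stated enrolment). Whether the sample size formula yields 120 is a separate matter.

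Suppose FNA is falsely malignant and FNB correctly benign. Correct scoring adds +1 to the FNB-minus-FNA count; the third row of the table adds −1. The change is 2/120 = 1.67 points. If the patient is left unclassified and contributes nothing, the change is 1/120 = 0.83 points.

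**Step 3. Effect over the trial.** The inputs below are assumptions, because the documents do not give them:

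- b: share of all patients who are truly benign, unresected and exposed to route (ii), 5% to 20%
- fA, fB: independent false-positive rates of techniques A and B
- q: share of false-positive patients that the imaging and course check does not catch, with caught patients scored correctly as benign

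True contribution to the difference B − A: b(fA − fB). 
Scored contribution: b(1 − 2q)(fA − fB). 
Shift against B: 2·b·q·(fA − fB). 
Expected mislabelled patients: 120·b·q·(fA + fB − fA·fB).

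| b | fA | fB | Shift, q = 1 | Shift, q = 0.5 | Mislabelled of 120, q = 1 |
|---|---|---|---|---|---|
| 5% | 5% | 2% | 0.30 | 0.15 | 0.4 |
| 10% | 5% | 2% | 0.60 | 0.30 | 0.8 |
| 10% | 10% | 2% | 1.60 | 0.80 | 1.4 |
| 20% | 5% | 2% | 1.20 | 0.60 | 1.7 |
| 20% | 10% | 2% | 3.20 | 1.60 | 2.8 |
| 5–20% | 2% | 2% | 0 | 0 | 0.2–1.0 |

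Shifts are in percentage points. Last unequal row: 2 × 0.20 × 1 × 0.08 = 0.032, or 3.2 points.

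Scoring caught patients as benign is kinder than the literal text, which leaves a caught discordant patient unclassified (fourth row of Step 1). Each such patient would add the 0.83 points of Step 2.

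**The case against.** Two stronger readings are tempting, and the documents support neither.

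The first is that a malignant reading proves itself at once in any unresected patient. Route (ii) is conjunctive: it also needs unresectable disease, fitting imaging and a fitting course. A benign lesion that is simply not operated on does not meet it, and a false positive that leads to resection is corrected under (i). What stands is that the check is undefined, has no minimum length and is not said to be blinded.

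The second is that the bias could use up the whole margin. Section 2.1 gives "sensitivities ranging from 64-95%, specificities ranging from 75-100" per cent for EUS-FNA. With 20% of 120 patients benign (24), FNA specificity of 75% and FNB specificity of 100%, 6 pairs flip and 2 × 6/120 = 10 points. This stacks worst cases. The 20% is in no document. The 75% is the bottom of a range for EUS-FNA in general, whereas this arm has ROSE, on which section 2.1 says yield depends heavily. All 24 patients would also have to be classed as unresectable, with none resected or corrected. Nothing in the documents shows that the two specificities differ.

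It is also fair that most discordance probably comes from missed cancers, which (ii) scores correctly. If 80% of 120 (96) are malignant, FNA sensitivity of 64% to 95% means about 35 to 5 cancers missed by FNA, against 0 to 6 false positives among 24 benign at specificity 100% to 75%. Not all of these misses would be discordant, but false-positive discordance is likely the smaller part.

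Finally, unresectable patients have no surgical specimen, so some non-surgical reference is unavoidable. That justifies having a route (ii). It does not justify letting a contested study reading settle the contest, nor a benign route that no discordant patient can meet.

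**Conclusion.** The point holds in a limited form. For discordant pairs in disease classed as unresectable, the plan can take one of the two compared readings as its reference, and read literally it can never return a benign final diagnosis. This is a defect in a stated scoring rule, not just missing detail.

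Its likely size is modest. With 5% to 20% of patients benign and exposed, false-positive rates of 5% or 10% against 2%, and half to all of the false positives uncaught, the shift is 0.15 to 3.2 points: at most about a third of the 10-point margin. Equal false-positive rates give zero net shift, and the direction is unknown in advance. All of these inputs except the 120 and the margin are assumptions. The shift would not by itself span the margin in these scenarios, but it could matter to a result close to it. The rule should be changed.

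**What to change.** Add a rule to section 12 for unresected patients whose FNA and FNB readings disagree:

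- Base the final diagnosis on evidence other than the two study samples: imaging and clinical course over the same minimum 6 months as route (iii), or any other tissue obtained in routine care.
- State what imaging and course count as fitting malignant or benign disease.
- Have this judged from a record that does not show which technique read malignant.
- Allow a benign final diagnosis when that evidence supports it.

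Keep route (i), and keep (ii) and (iii) for concordant pairs.

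Keep discordant patients who remain unclassified in the denominator, and report the accuracy difference twice: with all of them scored malignant and with all scored benign. An analysis that excludes patients whose diagnosis rested on a discordant study sample is not a substitute. It would drop unresectable cancers that one technique found and the other missed, and pull the difference towards zero, which favours non-inferiority.

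The cost is a wording change and later classification of a few patients. Some may stay unclassified: follow-up is only as clinically needed, and section 7 allows further sampling only after inadequate biopsies, so 6-month information or other tissue may not exist for an adequate but discordant pair.

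### Benign criterion (iii) joins cytology and histopathology with 'and'; applied literally to the study samples, it leaves unresected benign lesions that only one technique diagnoses without a final diagnosis, and no dated 6-month check is set

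*Combined protocol and SAP*

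**What the plan says.** Section 12 (Endpoints, Primary) gives three routes to the final diagnosis. Route (i) is surgical pathology after resection. Route (ii) is "ii) cytological or histopathological diagnosis of malignancy in patients with unresectable disease with appropriate imaging and clinical course of disease". Route (iii) is "iii) cytological and histopathological diagnosis of benign disease with an appropriate clinical course of disease for minimum of 6 months". The endpoint is then "Diagnostic accuracy will be defined as (true positive + true negative)/all samples", and for comparing "diagnostic accuracy between two EUS sampling techniques, we will use McNemar's test".

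Section 7 gives every patient both techniques but handles the material differently. For the biopsy needle, "FNB samples will be placed directly into formalin containers and sent to be processed by surgical pathology". For aspiration, "FNA specimens will be processed for ROSE using standard techniques with bedside smear slide evaluation and liquid-based cytology and cell-block preparation". Extra sampling by any technique is allowed if biopsies remain inadequate after six passes.

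Section 8 schedules a telephone call at 24-48 hours for early adverse events and zero follow-up visits, and leaves longer follow-up to clinical indication. Section 12 also states that "Baseline demographics, pre-, intra- and post-intervention data will be prospectively collected on data collection forms", and Section 11.4 lists hospital records and clinical charts among the source documents.

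**The concern.** Two adjacent criteria use different connectives, and only (iii) appears to require two kinds of tissue diagnosis. Among the study samples, cytology is described only for FNA. If cytology therefore means the FNA sample and histopathology the FNB sample, benign truth in an unresected patient is defined as agreement between the two tests under comparison.

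The primary analysis is paired, and McNemar's test uses only pairs on which the techniques differ. A reference standard that cannot classify a benign lesion seen by only one technique removes exactly that information from this group. The documents do not say which samples must satisfy (iii), whether an FNA cell block counts as histopathology, or how a patient who meets none of (i) to (iii) is scored.

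Criterion (iii) also depends on at least 6 months of clinical course, and no dated check of that status is scheduled.

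**Working it through.** **Step 1. What each reading of (iii) keeps.** Consider an unresected lesion that is truly benign, with no tissue beyond the study samples. Resected lesions fall under (i) and are unaffected.

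| Study samples | Literal: both samples benign | FNA cell block counts as histopathology | 'And' means 'or' |
|---|---|---|---|
| Both benign | classified | classified | classified |
| FNA only benign | **not classified** | classified | classified |
| FNB only benign | **not classified** | **not classified** | classified |
| Neither benign | not classified | not classified | not classified |

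Under the literal reading every lesion classified by (iii) is correct on both techniques by construction. Under the second, only lesions that favour FNB are lost. The last row is lost under either connective, and McNemar's test ignores it in any case.

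**Step 2. Inputs for an illustration.** From Section 12: 120 patients before dropout (used only as a scale, not re-derived), 85% success for FNA with ROSE, and a 10-point margin. Assumed, because the documents do not give them: 15% discordance; the same accuracy in all patients; an unresected benign share f of 5, 10 or 20% of patients; no later tissue.

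With FNB truly at -10 points (85% against 75%), the paired cells are:
- both right: p11 = 0.725
- only FNA right: p10 = 0.125
- only FNB right: p01 = 0.025
- neither right: p00 = 0.125

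**Step 3. Literal reading.** Benign lesions contribute no discordant pairs, so the numerator of the difference is (1 - f) × (0.025 - 0.125).
- Unclassified patients excluded: divide by k = (1 - f) + 0.725f.
  - f = 5%: -0.095/0.98625 = -9.6 points
  - f = 10%: -0.090/0.9725 = -9.3 points
  - f = 20%: -0.080/0.945 = -8.5 points
- Unclassified patients kept in the stated denominator as neither true positive nor true negative: divide by 1, giving -9.5, -9.0 and -8.0 points.

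Expected discordant pairs fall from 120 × 0.15 = 18.0 to 17.1, 16.2 and 14.4. This is the same under either denominator. The chance that the two-sided uncorrected McNemar test finds FNB worse falls from 85% to 83, 81 and 75%.

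**Step 4. Who is lost at f = 20%.** There are 24 unresected benign patients, and 24 × (1 - 0.725) = 6.6 go unclassified under the literal reading. Of these, 24 × 0.15 = 3.6 are discordant and 24 × 0.125 = 3.0 are wrong on both samples.

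**Step 5. The other readings at f = 20%, FNB at -10.**
- Cell block counts: numerator -0.080 - 0.20 × 0.125 = -0.105. Excluding unclassified patients, -0.105/0.970 = -10.8 points; keeping them, -10.5.
- 'And' means 'or': numerator -0.100. Excluding, -0.100/0.975 = -10.3 points; keeping them, -10.0.

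If the techniques are truly equal at 85% (cells 0.775/0.075/0.075/0.075), the cell-block reading gives -0.20 × 0.075 = -0.015, divided by 0.970, or -1.5 points against FNB. The other two readings give 0.

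**Step 6. Follow-up.** Section 12 requires a course of at least 6 months; the only timed contact in Section 8 is at 24-48 hours. Chart and post-intervention data could supply the later status, but no date, source or rule for missing status is set.

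**The case against.** **The connective may be loose drafting.** The adequacy endpoint, "This will be defined as the proportion of samples in which a final histopathological diagnosis could be made", applies the histopathological label to both techniques, which weakens the idea that the label means FNB alone. If 'or' was intended, no discordant benign pair is lost. This stands, and it is why the claim is conditional on the reading.

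**Not every lost pair is discordant.** A reader might infer that they all are. In the 20% case, 3.0 of the 6.6 are wrong on both samples and are lost under either connective. Only the 3.6 are due to 'and'.

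**The losses are upper bounds.** Section 7 limits extra sampling by the endosonographer, but nothing bars later clinically indicated tissue, and (iii) does not say that its tissue must come from the study samples. This stands.

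**Excluding patients sits badly with the stated denominator.** This is correct, and keeping them removes the shift under the 'or' reading. It does not rescue the literal reading, where the difference moves further from -10 (to -8.0 at 20%).

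**Conflicting samples are not without a rule.** If either sample suffices, the imaging and clinical course in (ii) and (iii) would settle most conflicts. This is accepted.

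**The 6-month status is obtainable.** A reader might infer from zero visits that it cannot be known. The documents do not support that, because charts and post-intervention data are available. What is absent is a dated check.

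**Conclusion.** The point holds conditionally. Applied literally to the study samples, (iii) makes every unresected benign lesion that it classifies correct on both techniques, and leaves those diagnosed by only one without a final diagnosis. In the illustration a true -10 points becomes -9.6/-9.3/-8.5 with unclassified patients excluded, or -9.5/-9.0/-8.0 with them kept, at 5/10/20% unresected benign. These are upper bounds resting on the assumed benign share, 15% discordance, equal accuracy across patients and no later tissue. At 5% the effect is small.

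A reader might infer that the plan is biased towards non-inferiority. The documents do not establish that. The literal reading pulls the difference towards zero, which helps FNB if it is worse in these lesions and hurts it if it is better. The cell-block reading counts against FNB, and the 'or' reading loses no discordant benign pair. The text does not fix the reading, so neither direction nor size is fixed. It should be settled before results are known, because it bears on the primary endpoint and costs little to settle.

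**What to change.** Reword (iii) so that benign status does not require both study samples to be benign: a benign clinical and imaging course of at least 6 months with no malignancy subsequently confirmed, with any available benign tissue as support.

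Score each technique's study sample separately against the final diagnosis. Count a non-diagnostic or wrong sample as incorrect for that technique, and keep every patient in the denominator.

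Record one dated 6-month status, by chart review or telephone, for each unresected patient not already established as malignant under (ii). Where status is missing, report the accuracy difference with all such patients taken as benign and again with all taken as malignant.

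The cost is one record review or call per such patient, with no extra procedure. Benign status would rest more on clinical course than on tissue, and measured accuracy may move in either direction. The study samples would still contribute to (ii), which this change does not address.

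### Specimen adequacy is scored on histopathological diagnosis only, so as written an FNA diagnostic on cytology alone counts as inadequate and the comparison leans towards FNB

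*Combined protocol and SAP*

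**What the plan says.** Section 12 lists specimen adequacy as secondary endpoint 1 and defines it in one sentence: "This will be defined as the proportion of samples in which a final histopathological diagnosis could be made". Cytology is not mentioned there.

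A few lines earlier, the reference standard for the primary endpoint names the two kinds of diagnosis separately. For malignancy it accepts a "cytological or histopathological diagnosis of malignancy in patients with unresectable disease", given suitable imaging and clinical course. For benign disease it refers to "cytological and histopathological diagnosis of benign disease with an appropriate clinical course of disease for minimum of 6 months".

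Section 7 (Procedure Plan) sends the two specimens down different routes. For FNB: "FNB samples will be placed directly into formalin containers and sent to be processed by surgical pathology". For FNA: "FNA specimens will be processed for ROSE using standard techniques with bedside smear slide evaluation and liquid-based cytology and cell-block preparation".

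Tissue cores have their own endpoint, secondary 2: "This will be defined as the proportion of samples in which a visible histology core biopsy was obtained". Section 12 names McNemar's test for diagnostic accuracy. Its general rule for categorical variables is the chi-square or Fisher's exact test. The plan gives no expected adequacy rate and no power for adequacy.

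**The concern.** An adequacy endpoint should ask the same question of both techniques: did the material allow a diagnosis? This one asks whether it allowed a diagnosis of one kind. That is the only kind FNB is processed to give, and just one of the kinds FNA is processed to give. An FNA whose smear or liquid-based preparation settles the diagnosis, but whose cell block is scant, would be scored inadequate.

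The error runs in one direction, against the comparator. The trial is meant to inform whether on-site cytopathology can be dropped (Sections 1 and 2.2). An adequacy advantage for FNB that came from the definition would be cited in support of that conclusion.

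The unit is also unclear. The definition counts samples, yet each technique may take up to three passes in a patient. If passes were counted singly, correlated results would be treated as independent.

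**Working it through.** **Step 1: the definition against the specimen routes.** The plan states no adequacy figure, so there is nothing to reproduce.

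| Material that gives the diagnosis | Adequate as written? |
|---|---|
| FNB, surgical pathology | Yes |
| FNA, smear or liquid-based cytology only | No: cytological, and the section keeps that term apart from histopathological |
| FNA, cell block | Not stated |

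No line of the table can wrongly fail a diagnostic FNB. The second line, and possibly the third, can wrongly fail a diagnostic FNA.

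**Step 2: how large the effect could be.** Inputs:

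- Pairs: 120, the evaluable number in Section 12. Section 7 has both techniques performed in every patient.
- True diagnostic yield: 85% for both techniques. Section 12 gives 85% as the FNA success rate. Using it as the yield of each technique is my assumption.
- Share *s* of diagnostic FNA samples that are diagnostic on cytology only: not in the documents. Assumed range 0% to 40%.
- Results of the two techniques independent within a patient: assumed.

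Formulas:

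- Measured FNA adequacy = 0.85 × (1 − s). Measured FNB adequacy = 0.85.
- Gap = 0.85 − 0.85 × (1 − s) = 0.85 × s.
- Expected pairs with FNB adequate and FNA not = 120 × 0.85 × [1 − 0.85 × (1 − s)].
- Expected pairs with FNA adequate and FNB not = 120 × 0.85 × (1 − s) × 0.15.

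The chance of significance is from 20,000 simulated trials, McNemar's test at two-sided 0.05 without continuity correction (exact version in brackets).

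| s | FNA adequacy | Gap, points | Chance of a significant result |
|---|---|---|---|
| 0% | 85.0% | 0 | 5% (3%) |
| 5% | 80.75% | 4.25 | 14% (10%) |
| 10% | 76.5% | 8.5 | 38% (33%) |
| 20% | 68.0% | 17.0 | 88% (85%) |
| 40% | 51.0% | 34.0 | about 100% |

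Expected discordant pairs:

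- At s = 10%: 120 × 0.85 × 0.235 = 24.0 against 120 × 0.765 × 0.15 = 13.8. The McNemar statistic is 10.2² / 37.7 = 2.8, p about 0.10.
- At s = 20%: 120 × 0.85 × 0.32 = 32.6 against 120 × 0.68 × 0.15 = 12.2. The statistic is 20.4² / 44.9 = 9.3, p about 0.002.

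**Step 3: does the choice of test matter?** McNemar's test is not named for adequacy, so the plan's general rule may send this endpoint to chi-square. At s = 20%, 102/120 against 82/120 gives p of about 0.002 there too. The problem lies in the definition, not the test.

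**Step 4: after correction.** If cytology counts for both techniques, the expected gap at equal true yield is 0 points, and the chance of a significant result returns to about 5%.

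**The case against.** The best defence is loose wording: the authors may have meant any final pathology diagnosis. The protocol is loosely worded elsewhere. Sections 2.1 and 2.2 compare FNA with ROSE to itself, and the design is single-center in Section 1 and multicenter in Section 1.1. The reference standard joins the two kinds of diagnosis with *or* for malignancy and *and* for benign disease, without explanation. This reading is possible, but no text supports it, and the authors did name cytology where they wanted it to count. If it is what they meant, the sentence still needs changing so that assessors score alike.

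Two further limits stand. FNA also yields a cell block; if that counts as histopathological, only samples diagnostic on smear or liquid-based cytology alone are lost. And the endpoint is secondary, with no margin or power of its own.

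Some stronger readings are tempting but not supported:

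- *Adequacy merely repeats the core endpoint.* The overlap is partial. A visible core can be non-diagnostic, and a cell block could be diagnostic without a visible core.
- *The background concedes that FNA must fail.* Section 2.1 says "The standard EUS-FNA does not routinely provide core biopsy specimen with preserved tissue architecture". That concerns architecture; it does not say FNA cannot support a pathological diagnosis.
- *A 20% share means 24 of 120 patients discordant one way and none the other, p about 1 in 10 million.* That needs the share to apply to all patients, FNB to succeed in all 24, and no discordance the other way. It is an extreme case. Independent pairs give about 33 against 12.
- *The same FNA is certainly a true positive on the primary endpoint.* Section 12 sets out how the final diagnosis is reached. It does not say how each technique's own result is classified.
- *The endpoint definition also governs when sampling stops.* Sections 7 and 8 use adequacy for that without defining it, and nothing links the two.

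The unclear unit is not special to this endpoint: the primary definition also counts samples, and no per-pass analysis is stated.

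**Conclusion.** The point holds as a definitional bias in one secondary endpoint. Read as written, the rule scores an FNA diagnostic on cytology alone as inadequate, and it can only favour FNB. The non-inferiority conclusion rests on diagnostic accuracy, which this definition does not touch.

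The size cannot be determined from the documents. It depends on the cytology-only share, which is not given, and on how a cell block is classed. Under the assumptions in the working, the gap runs from nothing at a 0% share, through 8.5 points at 10%, to 17 points at 20%. At a share of 5% or less, a significant false difference is unlikely (about 14% or lower); at 20% it is likely (about 88%). The gap does not depend on the independence assumption, but the chance of significance does: if the two techniques tend to succeed in the same patients, the same gap is more easily declared significant. The point should be settled before the data are analysed.

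**What to change.** Replace the adequacy sentence in Section 12 with: *the proportion of patients in whom the specimen from that technique (all passes combined) allowed a final cytological (smear, liquid-based cytology or cell block) or histopathological diagnosis.* Name a paired test for it, such as McNemar's, because both techniques are used in every patient. Leave tissue architecture to secondary endpoint 2.

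This settles the status of cytology and of the cell block, and fixes the patient, per technique, as the unit. It costs one sentence plus the naming of the test, with no change to procedures or sample size. The downside is that any FNB advantage on this endpoint may look smaller.
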